## 5.2 Exclusion criteria

Patients must not enter the study if any of the following exclusion criteria are fulfilled.

- 
1. Patients receiving any chemotherapy, radiotherapy (except for palliative reasons), or any other anti-cancer therapy within 4 weeks from the last dose prior to study randomisation (or a longer period depending on the defined characteristics of the agents used). Patients may continue the use of bisphosphonates for bone metastases, and corticosteroids provided the dose is stable before and during the study and these must have been started at least 4 weeks prior to the beginning of study treatment. Patients will be allowed to continue on hormone replacement therapy and on Luteinizing Hormone-Releasing Hormone (LHRH);
  2. Patients with symptomatic uncontrolled brain metastases. A scan to confirm the absence of brain metastases is not required. The patient can receive a stable dose of corticosteroids before and during the study as long as these were started at least 4 weeks prior to enrolment;
  3. Major surgery within 2 weeks of starting the study and patients must have recovered from any effects of any major surgery;
  4. Patients considered a poor medical risk due to a serious, uncontrolled medical disorder, non-malignant systemic disease or active, uncontrolled infection. Examples include, but are not limited to, uncontrolled ventricular arrhythmia, recent (within 3 months) myocardial infarction, unstable spinal cord compression (untreated and unstable for at least 28 days prior to study entry), superior vena cava syndrome, pure red cell aplasia, or any psychiatric disorder that prohibits obtaining informed consent
  5. Patients unable to swallow orally administered medication and patients with gastrointestinal disorders likely to interfere with absorption of the study medication (e.g. invasive pancreatic cancer, partial bowel obstruction or malabsorption);
  6. Pregnant or breastfeeding women;
  7. Immunocompromised patients, eg, patients who are known to be serologically positive for human immunodeficiency virus (HIV) and are receiving antiviral therapy;
  8. Patients with known hepatic disease (ie, Hepatitis B or C);
  9. Persistent toxicities (NCI-CTCAE grade 2 or greater) caused by previous cancer therapy (excluding alopecia).
  10. Involvement in the planning and/or conduct of the study (applies to both AstraZeneca staff and/or staff at the study site);
  11. Previous randomisation of treatment in the present study;

- 
12. Treatment with any investigational product during the last 14 days (or a longer period depending on the defined characteristics of the agents used);
  13. Patients with a known hypersensitivity to AZD2281 or any of the excipients of the product (Co-povidone, Gelucire);
  14. Patients currently experiencing seizures or who were currently being treated with only anti-epileptics for seizures (use of anti-epileptic drugs to control pain is allowed in patients not suffering from seizures unless drug is excluded due to CYP3A4 induction - phenytoin, carbamazepine, phenobarbital, see Section 6.3.1.
  15. Patients receiving the following classes of inhibitors of CYP3A4 (see Section 6.3.1 for guidelines and wash out periods).
    - Azole antifungals
    - Macrolide antibiotics
    - Protease inhibitors
  16. Patients with myelodysplastic syndrome/acute myeloid leukaemia (Group 8 only).
  17. Patients who are platinum refractory (Group 8 only).
  18. Patients who have previously received a PARP inhibitor (including AZD2281) (Group 8 only).

### **5.3 Restrictions**

1. Patients of child bearing potential and their partners, who are sexually active, must agree to the use of two highly effective forms of contraception throughout their participation in the study and for 3 months after last dose of study drug(s).

Condom with spermicide

and one of the following

oral contraceptive or hormonal therapy (eg, hormone implants)

Placement of an intra-uterine device (see [Appendix G](#) as consideration should be given to the type of device/system used)

Appendix G provides details of acceptable birth control methods to be used within the study.

- 
2. Male patients must refrain from fathering a child or donating sperm during the study and for 3 months following the last dose of AZD2281.
  3. No other chemotherapy or other novel agent is to be permitted during the course of the study for any patient. Palliative radiotherapy is allowed for pre-existing small areas of painful metastases that cannot be managed with local or systemic analgesics as long as no evidence of disease progression is present.
  4. An increased risk of infection by the administration of live virus and bacterial vaccines has been observed with conventional chemotherapy drugs. Effects with AZD2281 are unknown and therefore they should not be administered to patients in any treatment group.
  5. *In vitro* data have shown that the principal enzyme responsible for the formation of the 3 main metabolites of AZD2281 is CYP3A4 and consequently, although the contribution of metabolic clearance to total drug clearance in man is currently unknown, to ensure patient safety all patients must avoid concomitant use of drugs, herbal supplements and/or ingestion of foods known to modulate CYP3A4 enzyme activity (see Section 6.3.1) from the time they enter the screening period until 30 days after the last dose of study medication.
  6. Refrain from eating star fruit (averrhoa carambola) while taking the study medication.
  7. Patients who are blood donors should not donate blood during the study, and for 3 months after the last dose of study medication.
  8. PK phase only (cohorts 1 to 3) (N/A for Groups 1-8): Patients should not lie down during the absorption phase (from dose administration until 2 hours after dosing).

#### **5.4 Procedures for handling incorrectly included patients**

**Patients that do not meet the inclusion/exclusion criteria for a study should not, under any circumstances, be enrolled into the study – there can be no exceptions to this rule.**

Where patients that do not meet the study criteria are enrolled in error, incorrectly randomised, or where patients subsequently fail to meet the criteria for the study post enrolment, the procedures included in the protocol for the discontinuation of such patients must be followed. Once the error is identified a discussion must occur between the AstraZeneca Study Team Physician and the Investigator regarding whether to continue or discontinue the patient from the study. Once a decision is made, Investigators need to ensure they comply with all applicable requirements for human patient protection and ethical review. The AstraZeneca Study Team Physician is to ensure all such decisions are appropriately documented. In situations where an agreement cannot be reached with the Investigator in terms of how to manage the patient going forward, the patient should have their study medication stopped and be discontinued from the study.

## 5.5 Discontinuation of patients

### 5.5.1 Criteria for discontinuation

Patients may be discontinued from study treatment and assessments at any time. Specific reasons for discontinuing a patient are given below:

Discontinuation from the study:

- Voluntary withdrawal by the patient who is at any time free to discontinue their participation in the study, without prejudice to further treatment;
- Risk to patients as judged by the Investigator and/or AstraZeneca;
- Severe non-compliance to protocol as judged by the Investigator and/or AstraZeneca;
- Incorrectly enrolled patients, ie, the patient does not meet the required inclusion/exclusion criteria for the study;
- The patient becomes pregnant;
- Patient lost to follow-up.

Discontinuation from study treatment:

- **PK Phase:** Any NCI-CTCAE grade 3 or 4 events that have not reverted to NCI-CTCAE grade 1 or less within 2 weeks (14 days)
- **Continued Supply Phase:** Any NCI-CTCAE grade 3 or 4 events that have not reverted to NCI-CTCAE grade 1 or less within 4 weeks (28 days). (At the Investigator's discretion, following dose interruption, patients may be considered for dose reductions, providing they have not already undergone the maximum number of dose reductions allowed for guidelines see [Table 9](#) and [Table 10](#) for AZD2281. However, if upon re-challenging with AZD2281 at the lowest reduced dose any NCI-CTCAE grade 3 or 4 AEs recur, the patient must be discontinued (refer to Section [6.2.3.2](#)).

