- d AEs must be collected from the time of informed consent, throughout the treatment period and up to and including the follow-up period. All ongoing AEs must be monitored until resolution unless, in the Investigator's opinion, the condition is unlikely to resolve due to the patient's underlying disease. After discontinuation from treatment, patients must be followed up for all existing and new AEs for 30 calendar days (if SAEs, they must be reported to AstraZeneca within 24 hours) and followed until resolution unless, in the opinion of the Investigator, the condition is unlikely to resolve due to the patient's underlying disease.
- e For all patients enrolled into Groups 3 to 7 blood samples will be collected on Day 1 at the following timepoints: Pre-dose, 0.25, 0.5, 1, 1.5, 2, 3, 4, 6, 8, 10, 12 hours after morning dosing and on day 8 and Day 15 at the following timepoints: Pre-dose and 1 hour after morning dosing.
- f For the additional patients that are recruited to Groups 3 onwards, blood samples will be collected on Day 29 at the following timepoints: pre-dose and post-dose between 0 - 0.5 hours, 0.5 to 1.5 hours, 1.5 - 3 hours, 3 - 6 hours, 6 - 8, and 8-12 hours.
- g For the additional patients that are recruited to Group 6 and 7, blood samples will be collected on Day 29 and Day 57 at the following timepoints: pre-dose and post-dose between 0 - 0.5 hours, 0.5 to 1.5 hours, 1.5 - 3 hours, 3 - 6 hours, 6 - 8, and 8-12 hours.
- h For the additional patients recruited to Group 6, 7 and 8, follow-up tumour assessments will be performed every 8 weeks (+/-1 week) until disease progression or study end (Tumour assessments for Group 8 patients should be stopped after Cycle 5). Any other sites at which new disease is suspected should also be appropriately imaged. If scans are performed outside of scheduled visit  $\pm$  1 week window interval and the patient has not progressed, every attempt should be made to perform the subsequent scans at their scheduled time points. Patients must be followed until progression regardless of whether study treatment is discontinued or delayed and/or protocol violation. A repeat scan is needed at the next scheduled tumour assessment (at least  $\geq$  4 weeks) for confirmation of a PR or CR by RECIST. Radiological examinations performed in the conduct of the study should be retained at site as source data and may be collected by the sponsor if required.

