#### 7.3.5.5 CT or MRI scans (RECIST)

The RECIST guidelines ([Therasse et al 2000](#)) for measurable, non-measurable, target and non-target lesions, and the objective tumour response criteria (complete response (CR), partial response (PR), Stable disease (SD) or progression of disease (PD)) are presented in [Appendix F](#). The RECIST criteria will be used to programmatically determine best overall response, PFS and duration of response. Patients with non-measurable disease only at baseline are excluded from Group 1 within the Continued supply phase expansion.

Baseline and follow-up contrast-enhanced CT scans of chest, abdomen and pelvis for breast cancer and abdomen and pelvis for ovarian cancer with other regions as clinically indicated for the assessment of disease. All baseline radiological tumour assessments must be performed no more than 28 days before the start of study treatment. Scans that were performed as part of standard of care prior to signature of the informed consent form can be analysed for the purposes of the study if they were performed within the correct time frame and of sufficient quality. Subsequent tumour assessments according to RECIST should be performed at the end of every 2 months (8 weeks +/-1 week) according to the planned study schedule (see [Table 6](#) and [Table 7](#)) up to objective progression by RECIST. Any other sites at which new disease is suspected should also be appropriately imaged. Patients must be followed until RECIST disease progression. (Group 8 only: RECIST assessments should stop after Cycle 5).

Radiological examinations performed in the conduct of the study should be retained at site as source data and may be collected by the sponsor if required.

All measurable lesions confirmed and assessed by radiological methods (CT or MRI scans) up to a maximum of 5 lesions per organ and 10 lesions in total, representative of all involved organs, should be identified as target lesions, recorded and measured at baseline, and at the time points specified in the protocol.

Non-target lesions will also be monitored throughout the study, and an overall assessment of response will be made; complete response, incomplete response/stable disease or progression. Details of any new lesions will also be recorded.

Tumour assessment will be performed in accordance with the protocol schedule until evidence of one of the following:

- Progression of disease by RECIST
- Death without evidence of progression

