### **12.3.3 Progression Free Survival**

PFS is defined as the time from randomisation to the earlier date of assessment of objective progression (per RECIST criteria) or death by any cause in the absence of progression. Patients without a progression event and still alive at the time of analysis will be censored at the time of their last evaluable objective tumour assessment. This includes patients who are lost to follow up or who withdraw consent.

If at any follow-up visit  $> 1/3$  of the target lesions recorded at baseline are missing then target lesion response will be not-evaluable (NE) (unless the sum of the longest diameters [LDs] of non-missing target lesion LDs would result in PD).

If  $\leq 1/3$  of lesions recorded at baseline are missing then the results will be scaled up (based on the baseline sizes) to give an estimated sum of diameters and this will be used in calculations.

A complete response will not be permissible at a visit response where there is missing data.

Objective progression is defined as at least a 20% increase in sum of longest diameters of the target lesions (compared to previous minimum sum) or an overall non-target lesion assessment of progression or a new lesion.

Patients are to have radiological scans until objective progression, regardless of whether they discontinue their randomised therapy or take another anti cancer therapy prior to progression.

Tumour assessments for Group 8 patients should be stopped after Cycle 5 (week 16). Dates of progression and death will be defined as follows:

- The actual date of progression will be used in the analysis regardless of whether the patient had previously discontinued all or part of their randomised therapy, started another anti cancer therapy, the event occurred between scheduled visits or previous

visits were not evaluable due to partially, or completely missing tumour assessments. This also applies to patients who die in the absence of progression.

- If radiological assessments take place on multiple dates at a visit then the date of progression used for analysis will be the earliest of target lesions or non-target lesion or new lesion dates, regardless of which component contributed to progression.

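### Sections 5.5.1 and 5.4 let patients leave the study and its assessments for risk, severe non-compliance or incorrect enrolment, while the imaging rules require scans to progression; the conflict can bias the descriptive PFS and tumour-size comparisons

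*Protocol*

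**What the plan says.** Section 5.5.1 opens with "Patients may be discontinued from study treatment and assessments at any time". It then keeps two lists. The list for leaving the study includes "Risk to patients as judged by the Investigator and/or AstraZeneca", "Severe non-compliance to protocol as judged by the Investigator and/or AstraZeneca" and "Incorrectly enrolled patients, ie, the patient does not meet the required inclusion/exclusion criteria for the study", next to voluntary withdrawal, pregnancy and loss to follow-up. The list for stopping study treatment covers only grade 3 or 4 events that do not resolve in time or that recur at the lowest reduced dose.

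Section 5.4 asks for a discussion between the sponsor's physician and the investigator about an incorrectly included patient. If they cannot agree, "the patient should have their study medication stopped and be discontinued from the study".

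The imaging rules read differently:

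- Table 7 footnote h (Groups 6, 7 and 8), with the same sentence in Table 6 footnote g (Group 1): "Patients must be followed until progression regardless of whether study treatment is discontinued or delayed and/or protocol violation".
- Section 12.3.3: "Patients are to have radiological scans until objective progression, regardless of whether they discontinue their randomised therapy".
- Section 7.3.5.5: "Tumour assessment will be performed in accordance with the protocol schedule until evidence of one of the following". The three ends it then lists are RECIST progression, death without progression, and withdrawal of consent.

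In Group 8, tumour assessments stop after Cycle 5 for everyone.

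**The concern.** A Group 1 or Group 6 patient removed for severe non-compliance can be off study and unscanned under Section 5, yet due for a scan every 8 weeks under the schedule. A site has to choose, and different sites may choose differently.

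The choice affects the data. Under 12.3.3 a living patient without progression is censored at the last evaluable scan, and there is no separate rule for someone removed by the investigator or sponsor. Kaplan-Meier estimation assumes that censored patients have the same outlook as those who remain. Patients judged to be at risk, or severely non-compliant, may not. The tablet/capsule comparison is open-label, so the judgement behind a removal is made with the arm known.

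Efficacy is secondary, but the protocol uses it. Section 2.3 cites apparently lower anti-tumour activity among the reasons for exploring tablet doses above 200 mg bid. Section 12.4.5 compares tumour size at eight weeks between the tablet arms and the capsule arm. Section 6.2.3.2 allows patients to switch arms if the data favour one.

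**Working it through.** **Step 1: the passages side by side.**

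| Situation | Sections 5.4 and 5.5.1 | Imaging rules |
|---|---|---|
| Severe non-compliance | May leave study and assessments | Footnotes: followed to progression despite protocol violation. 7.3.5.5: not an end of assessment |
| Judged risk | May leave study and assessments | Footnotes and 12.3.3: scans continue after treatment stops. 7.3.5.5: not an end |
| Incorrect enrolment | May leave study; does so by default under 5.4 if there is no agreement | 7.3.5.5: not an end |
| Withdrawal of consent | Leaves study | 7.3.5.5: an end. No conflict |

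The clash is most direct for non-compliance, because the footnotes name protocol violation. Section 12.3.3 names stopping therapy and other anti-cancer therapy, but not violations.

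**Step 2: whether another section settles it.** Section 5.5.2 sends discontinued patients to a 7-day or 4-week visit for the Table 5 evaluations. Table 5 has no tumour-assessment row. Section 6.1 bars re-entry after a patient discontinues participation. Neither restores the scans.

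**Step 3: weight of one patient.** Group 1 has 20 patients randomised 1:1, so 10 per arm, and one patient is 1/10 = 10%. Groups 6 and 7 have about 15 per arm, so one patient is 1/15 = 6.7%.

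**Step 4: size of the bias.** The protocol gives no PFS median, removal rate or event count, so there is no figure of its own to reproduce. The assumptions are:

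- Exponential PFS with a median of 6 months. Section 4.2 says that median time on treatment before progression approached 6 months in previous studies.
- A fraction f = 0.10 to 0.20 of those event-free at 2 months is removed then.
- Removed patients have r = 1.5 to 3 times the hazard afterwards.

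With b = ln 2/6 = 0.1155 per month, S(2) = exp(-2b) = 0.794 and exp(-4b) = 0.630.

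- Kaplan-Meier estimate with removed patients censored at month 2: 0.794 × 0.630 = 0.50.
- True 6-month PFS: S(2) × [(1 - f) exp(-4b) + f exp(-4rb)].

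| f | r | Calculation | True value | Overstatement |
|---|---|---|---|---|
| 0.10 | 1.5 | 0.794 × (0.567 + 0.050) | 0.49 | 1 point |
| 0.20 | 1.5 | 0.794 × (0.504 + 0.100) | 0.48 | 2 points |
| 0.10 | 3 | 0.794 × (0.567 + 0.025) | 0.47 | 3 points |
| 0.20 | 3 | 0.794 × (0.504 + 0.050) | 0.44 | 6 points |

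With r = 1 the true value is also 0.50 and the bias is nil.

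**Step 5: a worst case by simulation.** This used 4,000 simulated arms, a median of 24 weeks and scans every 8 weeks. One to three patients per arm were removed in the very interval in which they progressed and were censored at their last clean scan. With full follow-up, 24-week PFS averages about 0.50.

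| Arm size | 1 removed | 2 removed | 3 removed |
|---|---|---|---|
| 15 | 0.52 (+2 points) | 0.54 (+4) | 0.57 (+6) |
| 10 | 0.53 (+3) | 0.56 (+6 to 7) | 0.60 (+10) |

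**Step 6: tumour size.** A patient removed before the week-8 scan has no week-8 value. Removal at 2 months or later, as in Step 4, leaves that comparison essentially untouched.

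**The case against.** The strongest reply is that the intent is clear. The imaging passages agree with each other, and against them stands a general list that only says patients may be discontinued. Section 5.4 allows an incorrectly included patient to continue after discussion. An ordinary protocol violation is not the same as severe non-compliance, so the footnotes and 5.5.1 overlap only in part. Section 5.5.2 uses study and treatment discontinuation loosely, so 5.5.1 need not be read as an order to stop imaging.

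The consequence is also limited. PFS is summarised by Kaplan-Meier without a test, and 12.4.5 makes no formal sample-size calculation. Ignoring censoring, a 95% interval around 50% is ±1.96 × √(0.25/15), about 25 points, with 15 patients, and about 31 points with 10. The assumed removal rates and hazards have no source in the protocol, and incorrect enrolment has no evident link to prognosis.

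Most of this stands, and it limits the claim. A reader might infer that the plan removes such patients as a rule, or that PFS is informatively censored as it stands. The permissive wording does not support either; it shows only that this can happen. What the reply does not remove is the conflict itself. A site that follows Section 5 finds no instruction there to keep scanning. Wide intervals describe random error; they do not excuse an avoidable systematic one.

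**Conclusion.** The conflict is real and should be reconciled. If Section 5 is followed, affected patients in Groups 1, 6 and 7 are censored at their last scan, as are Group 8 patients up to Cycle 5. Those removed before week 8 also drop out of the week-8 tumour-size comparison.

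The descriptive comparisons are biased only if removal is related to prognosis. The effect is then about 1 to 6 points on 6-month PFS under the assumed 10-20% removal and 1.5- to 3-fold hazard. In the deliberately extreme case where every removal coincides with progression, it is about 2 to 6 points with 15 per arm and 3 to 10 points with 10. It is about nil if removal is unrelated to prognosis. No error rate or formal decision rule depends on it.

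Two further readings should not be pressed. Different removal rates by arm are possible in an open-label study, but nothing in the protocol shows that they would occur. The pregnancy wording is not a clear contradiction either: stopping treatment at once, as the table footnotes require, is compatible with also leaving the study under 5.5.1.

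**What to change.** Reconcile the passages in 5.5.1 and 5.4 with a statement along these lines:

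> Stopping study treatment, or being found non-compliant or ineligible, does not by itself end the collection of outcome data. Tumour assessments and survival status continue as set out in Tables 6 and 7 and section 7.3.5.5 unless the patient withdraws consent or is lost to follow-up.

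The Group 8 stop after Cycle 5 stays as it is. The opening sentence of 5.5.1 and the pointer from 5.5.2 to Table 5 should be checked against this statement, since Table 5 has no tumour assessment.

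How patients at risk or pregnant patients are managed, including whether they are imaged, is for the sponsor and investigators to settle when they reconcile the passages.

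The cost is a wording amendment and continued follow-up of a few patients, which the schedules already require.
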